10.7. Responsibilities of the HREC/IRB

The sponsor, through their independent safety monitoring arrangements, has the primary responsibility for monitoring the ongoing safety of the IMP. The HREC/IRB should be satisfied that the sponsor's arrangements are sufficiently independent and commensurate with the risk, size and complexity of the trial. The approving HREC/IRB should:

- Assess the safety of proposed trials, including whether the evaluation of the anticipated benefits and risks is satisfactory and ensure that the sponsor has proportionate systems in place to mitigate and manage any identified risks.
- Satisfy itself that the sponsor's ongoing safety monitoring arrangements are adequate, including the justification for appointing/not appointing a DSMB and any 'stopping rules' or criteria for withdrawing individual participants from the trial.

10.8. Responsibilities of the TGA and FDA

The TGA or FDA may:

- Conduct an audit of a clinical trial where necessary on safety grounds; and
- Stop a trial where that action is in the public's interest.

10.9. Data and Safety Monitoring Board

An independent, suitably qualified DSMB will be convened and will meet quarterly during the study to review safety data during the conduct of the clinical investigation. The DSMB will include both an independent ophthalmologist (retinal specialist) and psychiatrist.

The DSMB will meet prior to the start of the study, quarterly during enrollment and follow-up and at trial end to review safety data. The Board will be responsible for recommendations related to the safety of participants and the continuation of the study. The Board will review SAEs for the duration of the trial and all pregnancies and evaluate any safety issues with respect to trial conduct. A separate DSMB charter will be drafted for the study. The Board will be blinded to participants' actual randomized group assignments but may request at any time that the blind be broken by the Data Management Site, if concerns arise from the blinded data. *Ad hoc* meetings will be convened if SAEs occur that are considered at least possibly related to the IMP.

10.10. Safety Surveillance During the Study

Participants will be monitored and safety data collected by way of clinical interviews, observations and examinations and laboratory evaluations. Time points and the specific data collected for each of these evaluations are described in [Section 8](#) and [Section 9](#).

Any signs and symptoms of ADRs to IMP will be treated symptomatically.

10.11. Adverse Events

The collection, evaluation and reporting of AEs/ADRs arising from this clinical study will be performed in accordance with:

- Detailed guidance on the collection, verification and presentation of AE/ADR reports arising from clinical trials on medicinal products for human use ('CT-3') ([2011/C 172/01](#));
- [ICH guideline E2A](#): Clinical Safety Data Management: Definitions and Standards for Expedited Reporting; and
- [ICH guideline E2F](#): Note for guidance on DSUR.

The definitions of AEs, ADRs, SAEs, and SUSARs are given below. It is of the utmost importance that all staff involved in the conduct of clinical research is familiar with the content of this section.

10.11.1. Definitions

An **adverse event (AE)** - any untoward medical occurrence in a patient or clinical trial participant administered an IMP and that does not necessarily have a causal relationship with the treatment.

An **adverse drug reaction (ADR)** – any untoward and unintended response to an IMP related to any dose administered. Any AE judged by either the reporting investigator or the sponsor as having a reasonable possibility of a causal relationship to an IMP would qualify as ADRs. The expression “reasonable causal relationship” means, there is evidence or argument to suggest a causal relationship.

The following are examples of types of evidence that would suggest a causal relationship between the IMP and the AE:

- A single occurrence of an AE that is uncommon and known to be strongly associated with drug exposure (e.g., angioedema, hepatic injury, Stevens-Johnson Syndrome);
- One or more occurrences of an AE that is not commonly associated with drug exposure, but is otherwise uncommon in the population exposed to the drug (e.g., tendon rupture).
- An aggregate analysis of specific AEs observed in clinical trials (such as known consequences of the underlying disease or condition under investigation or other AEs that commonly occur in the study population independent of drug therapy) that indicates those events occur more frequently in the drug treatment group than in the a concurrent or historical control group.

An AE/ADR may be:

- A new symptom, sign or medical condition;

- A new diagnosis;
- An intercurrent illness or accident;
- An exacerbation of a pre-existing medical condition/disease;
- The recurrence of a disease;
- An increase in frequency or intensity of a pre-existing episodic disease or symptom;
- An abnormal assessment (e.g., change on physical examination) if it represents a clinically significant finding that was not present at study start or worsened during the course of the study; or
- An abnormal laboratory assessment or change in a laboratory parameter.

Borderline abnormal laboratory findings and other objective assessments should NOT be routinely captured and reported as AEs, as they will be collected and analyzed separately. However, abnormal laboratory findings or other objective measurements that meet the following criteria should be captured and reported in the AE section of the eCRF:

- The result meets the criteria for reporting as an SAE;
- The test result is associated with accompanying symptoms; and/or;
- It requires additional diagnostic testing or medical/surgical intervention; and/or;
- It leads to a change in trial dosing outside of protocol-stipulated dose adjustments, or discontinuation from the trial, significant additional concomitant drug treatment, or other therapy; and/or
- It is considered by the investigator or sponsor to be clinically significant or represent a clinically significant change from baseline.

Merely repeating an abnormal test, in the absence of any of the above conditions, does not constitute an AE/ADR. Any abnormal test result that is determined to be an error does not require reporting as an AE.

If a clinical diagnosis is associated with an abnormal laboratory finding, the relevant AE should be recorded as the diagnosis rather than the incidental laboratory finding (e.g. “hepatitis” should be recorded rather than “elevated transaminases”).

Surgical procedures themselves are not AEs; they are therapeutic measures for conditions, which may, or may not, be AEs/ADRs. Planned surgical measures permitted by the clinical trial protocol and the condition(s) leading to these measures are not AEs if the condition was present before inclusion in the trial. In the latter case the condition should be reported as medical history.

An ADR is regarded as an **unexpected adverse reaction** if its nature or severity is not consistent with the applicable reference safety information (Investigator’s Brochure). Events that add significant information on the specificity, severity or frequency of previously described reactions, are also regarded as unexpected.

The expectedness of an ADR is determined by the sponsor in the reference safety information and will be evaluated in the context of previously observed events, rather than on the basis of what might be anticipated from the pharmacological properties of a medicinal product.

For this protocol, the reference document is the [60P IB](#).

A **Serious Adverse Event/Reaction (SAE/SAR)** is defined as an event or reaction which:

- Results in death;
- Is life-threatening (the term "life-threatening" in the definition of "serious" refers to an event in which the participant was at immediate risk of death at the time of the event; it does not refer to an event which hypothetically might have caused death if it was more severe);
- Requires hospitalization or prolongs existing hospitalization, unless this is for:
 - Elective or pre-planned treatment for a pre-existing condition that is unrelated to the trial and has not worsened since the start of the IMP;
 - Treatment on an emergency outpatient basis for an event not fulfilling any of the definitions of an SAE given above and not resulting in hospital admission;
 - Cosmetic surgery or for social reasons or respite care in the absence of any deterioration in the participant's general condition;
- Results in persistent or significant disability/incapacity;
- Is a congenital abnormality/birth defect;
- Is considered medically important (medical and scientific judgment should be exercised in deciding whether other AE/ADRs are to be considered serious, such as important medical events that may not be immediately life threatening but may jeopardize the participant or may require intervention to prevent one of the other outcomes listed in the definition above. Examples of such events are: intensive treatment in an emergency room or at home for allergic bronchospasm; blood dyscrasias; convulsions that do not result in hospitalization; development of drug dependency or drug abuse); and
- For the purpose of this protocol an AE will be considered as serious should the AE constitute a possible Hy's Law case (defined as a participant with any value of ALT or AST greater than or equal to 3x upper limit of normal (ULN) together with an increase in bilirubin to a value greater than 2x ULN (>35% direct) and NOT associated cholestasis (ALP value less than 2x ULN).

A **non-serious** AE/ADR is any symptom or sign, which does not fulfill any of the above-mentioned seriousness criteria.

A **Safety Critical Adverse Event** is any adverse event and/or laboratory abnormality identified in the protocol as critical to safety evaluations that should be reported to the sponsor according to the reporting requirements specified in the protocol.

A **Significant Safety Issue (SSI)** is any safety issue that could adversely affect the safety of participants or materially impact on the continued ethical acceptability or conduct of the trial.

A **Suspected Unexpected Serious Adverse Reactions (SUSAR)** is any SAE where a causal relationship with the IMP is at least a reasonable possibility, but the event is not listed in the [60P IB](#).

An **Urgent Safety Measure (USM)** is any measure required to be taken in order to eliminate an immediate hazard to a participant's health or safety. This type of significant safety issue can be instigated by either the investigator or sponsor and can be implemented before seeking approval from HREC/IRBs or Institutions.

An **Unanticipated Problem Involving Risk to Subjects or Others** (UPIRTSO) is defined as any problem or event which, in the opinion of the local investigator, was unanticipated, places participants or others at a greater risk of harm than was previously known or recognized, and was possibly related to the research procedure.

An **Adverse Events of Special Interest (AESIs)** for this study are defined as:

1. Hepatic:
 - a. Possible Hy's law case: defined as a participant with any value of ALT or AST above 3x ULN together with an increase in bilirubin to a value higher than 2x ULN and not associated with cholestasis (ALP value less than 2x ULN) (to be reported as an SAE as detailed above);
 - b. Any ALT or AST above 3x ULN;
 - c. Any elevation in bilirubin 2x ULN;
 - d. Any AST or ALT above 2x ULN and (total bilirubin [TBL] >1.5x ULN); and
 - e. Any AST or ALT above 2x ULN with the appearance of fatigue, nausea, vomiting, right upper quadrant pain or tenderness, fever, rash and/or eosinophilia (eosinophil percent or count above the ULN).
2. Ophthalmic:
 - a. Functional change on microperimetry test showing an abnormality in the paracentral region forming a ring or partial ring.
 - b. New abnormality by FM-100 hue test.
 - c. Significant deterioration in the Mars letter contrast sensitivity test with a change exceeding 0.12 logCS.
 - d. Unexplained marked reduction of visual acuity ≥ 15 letters that persists for ≥ 2 visits separated by at least one week.
 - e. A ≥ 15 letter change [≥ 3 lines] change in ETDRS BCVA at 4 meters.
3. Hematologic
 - a. Methemoglobin > 10%.
4. Other:
 - a. Any other AE that, in the opinion of the investigator, is related to the IMP and may jeopardize the participant's safety.

Although not considered an AE, pregnancy in female participants will be reported as an **event of special interest** as per [Section 10.11.6](#).

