9.1.3. Medical, Surgical and Current Medical Conditions

Participants will provide a detailed medical, surgical, and medication usage during screening and again prior to IMP administration, in order to assess the eligibility of the participant for the study.

Any event or change in the participant's condition or health status prior to the initial administration of the IMP will be reported in the relevant medical history/current medical conditions section of the eCRF and not as an AE pre-dose.

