10.3. Study Pharmaceutical Sponsor

The sponsor also has an institutional responsibility to ensure participant safety and undertakes to promptly notify the concerned investigators, HREC/IRB, TGA and FDA of findings that could adversely affect the safety of participants included in the study, impact the conduct of the study, or alter the HREC/IRB approval/favorable opinion to continue the study. This includes the expedited reporting to these parties of all adverse drug reactions (ADRs) that are both serious and unexpected (SUSAR).

Under 21 CFR 312.50, sponsors are responsible for selecting qualified investigators, providing them with the information they need to conduct an investigation properly, ensuring proper monitoring of the investigation(s), ensuring that the investigation(s) is conducted in accordance with the general investigational plan and protocols contained in the IND, maintaining an effective IND with respect to the investigations, and ensuring that FDA and all participating investigators are promptly informed of significant new adverse effects or risks with respect to the drug. Additional specific responsibilities of sponsors are described in 21 CFR 312.

Under 21 CFR 312 (c)(1) IND safety reports, the sponsor must notify FDA and all participating investigators (i.e., all investigators to whom the sponsor is providing drug under its INDs or under any investigator's IND) in an IND safety report of potential serious risks, from clinical trials or any other source, as soon as possible, but in no case later than 15 calendar days after the sponsor determines that the information qualifies for reporting.

Specifically, the sponsor should:

- Ensure that the trial protocol has clear sections describing:
 - The assessment and management of risk (if not in an alternative document). The trial protocol and/or the safety monitoring plan, should describe the composition, roles and responsibilities of oversight committees and plans for ongoing safety monitoring;
 - Safety reporting definitions, procedures, responsibilities and reporting timelines; and
 - Any SAEs that do not require immediate reporting.
- Keep detailed records of all reported AEs and maintain up-to-date tabulations and/or line listings. The sponsor may be required to provide tabulations/line listings to the TGA and FDA on request.

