- When communicating safety information to investigators and/or HREC/IRBs, clarify the impact of each report on patient safety, trial conduct or trial documentation
- Assess and categorise the safety reports received from investigators, and report all SUSARs occurring in participants to the TGA and FDA under IND 129,656 (in accordance with (IAW) 21 CFR 312.32):

- For fatal or life threatening SUSARs, immediately, but no later than **7 calendar days** after being made aware of the case, with any follow-up information within a further 8 calendar days.
- For all other SUSARs, no later than **15 calendar days** after being made aware of the case.

When determining whether a SUSAR has occurred, where the sponsor's causality assessment conflicts with the assessment made by the site investigator, the site investigator's assessment cannot be downgraded by the sponsor (i.e., altered from 'related' to 'not related'). In this case, if an investigator's judgment triggers the reporting of a SUSAR, the opinion of both the investigator and the sponsor should be provided with any SUSAR report sent to the TGA and the FDA.

When reporting a SUSAR to the TGA and FDA, the blind should generally be broken by the sponsor (See Section D of [ICH guideline E2A Managing Blinded Therapy Cases](#)). In order to avoid introducing biases, the blind should be maintained for all other persons involved in the conduct or management of the trial, including those responsible for data analysis and/or interpretation of results.

- Review the IB at least annually and update it when new and relevant information becomes available;
- Provide the HREC/IRB and investigators with any update/addenda of the IB;
- Provide the HREC/IRB with an **annual safety report (i.e., drug safety update report [DSUR])** including a clear summary of the evolving safety profile of the trial. This report should allow the HREC/IRBs to assess whether ongoing safety monitoring is being conducted appropriately and that the trial's safety monitoring plans are being followed and where necessary, are being adapted to take into account new findings as the trial progresses.
- Ensure that all sponsor responsibilities for safety monitoring and reporting (e.g. reporting SUSARs and significant safety issues to the TGA and FDA) are appropriately allocated or delegated.

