10.11.2. Assessment and Recording of Adverse Events

It is the investigator's responsibility to document and report all AEs occurring in the clinical trial whether spontaneously reported by the participant, observed by the investigator (either directly or by laboratory or other assessments), or elicited by general questioning.

The period of observation for collection of AEs extends from the time of dosing (Day 1, Week 1 [Visit 2]) through the Week 64 follow-up visit. Those participants meeting the criteria for additional safety follow-up ([Section 8.5](#)) will be followed every 3 months thereafter to a maximum of 12 months until the AE resolves or stabilizes.

SAEs will be reported from the time of screening until 30 days following the EOS visit (Week 64) (if spontaneously reported by the participant). Serious adverse events experienced

after this 30-day period will only be reported if the investigator suspects a causal relationship with the study drug.

The following information should be recorded for all AEs:

- The name of the AE;
- The dates of onset and resolution of the event;
- The characteristics of the event (seriousness, intensity);
- The action taken in response to the event (including treatment required);
- The outcome of the event; and
- The relationship of the event to the study drug (causality assessment) and/or to study participation.

Standard toxicity grading

The medical assessment of AE severity of the study will be recorded in accordance with the Common Terminology Criteria for Adverse Events v 4.03 that went into effect June 14, 2010 ([CTCAE V4.03](#)). Note however, if the local site's normal blood pressure ranges overlap with that considered to be a grade 1 toxicity according to the CTCAE, that the upper limit of the local sites scale will be considered the cutoff for reporting an AE.

- Grade 1: Mild - asymptomatic or mild symptoms; clinical or diagnostic observations only; intervention not indicated;
- Grade 2: Moderate - minimal, local or non-invasive intervention indicated; limiting age-appropriate instrumental activities of daily living (ADL);
- Grade 3: Severe or medically significant but not immediately life-threatening; hospitalization or prolongation of hospitalization indicated; disabling; limiting self-care ADL;
- Grade 4: Life-threatening consequences; urgent intervention indicated.

Severity grading (AEs not included within [CTCAE V4.03](#))

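### Section 10.11.1 applies two different tests to the SUSAR label: the definition requires an event not listed in the IB, which is narrower than the protocol's own meaning of unexpected

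*Combined protocol and SAP*

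**What the plan says.** **Unexpected reaction (Section 10.11.1).** A reaction is unexpected "if its nature or severity is not consistent with the applicable reference safety information", which for this protocol is the 60P IB. The same paragraph then widens the test: "Events that add significant information on the specificity, severity or frequency of previously described reactions, are also regarded as unexpected". Expectedness is for the sponsor to determine.

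**SUSAR (Section 10.11.1, a little further on).** Such an event "is any SAE where a causal relationship with the IMP is at least a reasonable possibility, but the event is not listed in the"; the document meant is the IB. The protocol does not say whether a listing carries a given severity or frequency with it.

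**Sponsor's duty (Section 10.3).** Expedited reporting covers "adverse drug reactions (ADRs) that are both serious and unexpected (SUSAR"), with no condition about listing. The sponsor must "report all SUSARs occurring in participants to the TGA and FDA under IND 129,656", within 7 calendar days if fatal or life-threatening and 15 otherwise. Section 10.11.4 repeats these limits.

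**Site's duty (Section 10.2).** The investigator reports local SUSARs to the institution within 72 hours, on his or her own judgment that a SUSAR has occurred.

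**Events before the first dose.** Section 9.1.3 says that such events "will be reported in the relevant medical history/current medical conditions section of the eCRF and not as an AE pre-dose". Section 10.11.2 says that "SAEs will be reported from the time of screening until 30 days following the EOS visit".

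**The concern.** Two tests for one label can sort the same case differently. The label starts the 7- or 15-day reports to the TGA, FDA and HREC/IRB, the site's 72-hour report, and in general the breaking of the blind by the sponsor (Section 10.3). The cases that fall between the tests are reactions already described for the drug that turn out worse, or more frequent, than described. Those matter in a trial that doubles the studied exposure from 6 to 12 months in order to learn about long-term safety. Sites in two countries will work from these definitions, and Section 10.11 itself stresses that all staff must know them.

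The wording on events before the first dose raises a smaller question: Section 9.1.3 makes no exception for serious events, although SAE reporting has by then begun.

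**Working it through.** No sample size, power or rate is involved, so the check is a comparison of text.

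**Step 1. Apply both tests to a serious, related reaction.** Seriousness and causality are common to both, so only the last condition can separate them.

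| Reaction relative to the IB | Unexpected under 10.11.1, so a SUSAR under 10.3 | SUSAR under the listing wording |
|---|---|---|
| Not named | Yes | Yes |
| Named, consistent, nothing new | No | No |
| Named, but more severe than described | Yes | No |
| Named, but adds significant information on specificity or frequency | Yes | No |

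The tests agree on the first two rows and disagree on the last two. The listing test is therefore strictly the narrower one.

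**Step 2. See what else would catch the last two rows.**

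| Route | Reaches a regulator? | Clock | Limitation |
|---|---|---|---|
| Significant safety issue (10.3) | TGA and FDA | 15 days; 72 hours if an urgent safety measure | Needs a judgment about participant safety or trial conduct; the matching example is a DSMB recommendation |
| IND safety report (10.3) | FDA | 15 days | For potential serious risks; the TGA is not a named recipient |
| Other issue that may alter benefit–risk (10.11.4) | Health authorities | Expedited, no number of days | Needs a benefit–risk judgment |
| AESI report (10.11.5) | No | 24 hours | Goes to the medical monitor and project manager, with the sponsor copied |
| SAE notice (10.2, 10.11.4) | No | 24 hours | Goes to the sponsor and the DSMB |
| DSMB review (10.9) | No | Quarterly, or ad hoc for possibly related SAEs | Leads to recommendations |

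For a fatal or life-threatening reaction in the last two rows of the first table, the SUSAR clock is 7 days. The fixed regulatory clock on the other routes is 15 days, a difference of 15 − 7 = 8 days, unless an urgent safety measure has been taken. If none of the judgments in Step 2 is made, no regulatory clock starts.

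The significant-safety-issue text adds to the inconsistency. Its example speaks of an *expected* reaction becoming more frequent or severe, whereas Section 10.11.1 can class the same reaction as unexpected.

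**Step 3. Events before the first dose.** Section 9.1.3 governs which eCRF section holds the record. Section 10.11.2 sets two windows: AEs from dosing, SAEs from screening. A serious event during the screening period of up to 6 weeks can be entered in medical history and also sent as an SAE. Section 10.2 then takes it to the sponsor, and Section 10.11.4 takes it to the DSMB and the study database. Both rules can be followed; only the cross-reference is missing.

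**The case against.** The best defence is that the narrow reading takes one paragraph in isolation. The word *unexpected* is part of the name SUSAR and is defined earlier in the same section. The sponsor decides expectedness, and the sponsor's duty in Section 10.3 is framed as serious and unexpected. Section 10.3 ties SUSAR reporting to 21 CFR 312.32, and Section 10.11 places AE handling under CT-3 and ICH E2A. Every SAE also reaches the sponsor within 24 hours unless the protocol exempts it, so someone able to apply the wider test will normally see the case.

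Much of this stands, and it limits the harm. It does not remove the conflict. *Listed* is never explained, the 72-hour site report rests on the investigator's reading of the definition, and the other routes are slower, depend on a further judgment, or do not reach a regulator.

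Two stronger readings are tempting and are not supported.

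- A reader might infer from Tables 1 and 2 that expedited reporting is switched off for retinal disorder, keratopathy and suicide attempt, and take the SAE counts there as the size of the problem. Those tables count past SAEs; they do not show what the IB lists. The background text before Table 2 says the suicide attempt was considered unrelated to tafenoquine, and Section 2.1.1 reports that the keratopathy was judged benign and reversible. The routes in Step 2 also remain open.
- A reader might infer from Section 9.1.3 that a serious event at screening has no way to reach the sponsor or the DSMB. Section 10.11.2, with Sections 10.2 and 10.11.4, provides one.

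**Conclusion.** The definitions conflict, and the conflict should be removed. On its literal wording, the SUSAR definition leaves out serious, related reactions that are named in the IB but are worse than described or add significant information on specificity or frequency. Elsewhere the protocol treats these as unexpected and therefore as SUSARs. The remaining routes cover the gap only in part.

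The size is the class of events affected and up to 8 days on the clock for fatal or life-threatening cases handled by a 15-day route. It cannot be put as a number of cases. The conflict in wording does not depend on what the IB lists; how often it would matter does. Sections 2.3.2 and 5.5.1.2 describe several known effects, and Section 5.5 refers to the IB for full risks, so some listing is likely, but that is an assumption.

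The IB, the Study Safety plan, the safety manual and what appears to be the opening of Section 10.11.4 were not available. A clarification there cannot be excluded, although the two definitions in Section 10.11.1 would still differ. The wording in Section 9.1.3 is a minor consistency matter. The primary endpoint, the power and the tables of treatment-emergent events are unaffected.

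**What to change.** In the SUSAR definition of Section 10.11.1, replace the closing condition about listing in the IB with: *and the reaction is unexpected as defined above*. Do not restate the criteria in brackets; a paraphrase that departs from the paragraph on unexpected reactions would create a third test. Check that the Study Safety plan and the safety manual use the same wording.

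As a minor edit, add to Section 9.1.3: *SAEs from screening onward are also reported under Section 10.11.2*.

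The cost is one clause and one cross-reference in a protocol amendment, and at most a few more expedited reports. No assessment, dose or analysis changes.
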